7.8.2.1 Human Smoking Topography Parameters

The HST SODIM® device measures and records the flow and other per-puff parameters listed in Table 5, the per cigarette parameters shown in

Table 6 will be derived (representing average values or totals per cigarette).

Prior to calculation of the per cigarette parameters, the Sponsor HST group will validate the data and discard any invalid data. Only valid data for per-cigarette parameters will be part of the study database and will be analyzed.

Table 5. Human Smoking Topography – Per-Puff Parameters

Description	Variable	Unit
Puff number	Ni	
Puff volume	Vi	mL
Puff duration	Di	s
Average flow [Vi/Di]	Qmi	mL/s
Peak flow	Qci	mL/s
Inter puff interval	Ii	s
Sum of Ii and Di	DFi	s
Work [INT Pmi*FinalFlow*dt]	Wi	mJ
Average pressure drop	Pmi	mmWG
Peak pressure drop	Pci	mmWG
Average resistance [Pmi/Qmi]	Rmi	mmWG/mL/s
Peak resistance [Pci/Qci]	Rci	mmWG/mL/s

Table 6. Human Smoking Topography – Per-Cigarette Parameters

Description	Variable	Formula	Unit
Total number of puffs	NPC	$\sum Ni$	
Total puff volume	TVOL	$\sum Vi$	mL
Average puff volume	AvgVi	$\sum Vi / NPC, i=1 \dots NPC$	mL
Average puff duration	AvgDi	$\sum Di / NPC, i=1 \dots NPC$	s
Total puff duration	TDi	$\sum Di$	s
Average flow	AvgQmi	$\sum Qmi / NPC, i=1 \dots NPC$	mL/s
Peak flow	AvgQci	$\sum Qci / NPC, i=1 \dots NPC$	mL/s
Total inter puff interval	TII	$\sum Ii$	s
Average inter puff interval	AvgIi	$\sum Qci / NPC, i=1 \dots NPC$	s
Total smoking duration	TDFi	$\sum DFi$	s
Total Work	TWi	$\sum Wi$	mJ
Average Work	AvgWi	$\sum Wi / NPC, i=1 \dots NPC$	mJ
Average pressure drop	AvgPmi	$\sum Pmi / NPC, i=1 \dots NPC$	mmWg
Average Peak pressure drop	AvgPci	$\sum Pci / NPC, i=1 \dots NPC$	mmWg
Smoking Intensity	SMINT	TVOL/TDFi	mL/s

Data and information contained in this document are considered to constitute trade secrets and confidential commercial information, and the legal protections provided to such trade secrets and confidential information are hereby claimed under the provisions of United States law. No part of this document may be publicly disclosed without the written consent of Philip Morris International.

Description	Variable	Formula	Unit
Puffing Time Index	PTI	(100*TDi)/TDFi	%
Puff Frequency	PFeq	NPC/(TDFi/60)	Min-1

7.8.2.2 Visual Inspection of the Tobacco Plugs

All THS tobacco plugs collected during the study will be sent to the Sponsor for subsequent visual inspection to determine whether combustion occurred during product use (Section 9).

7.8.3 Questionnaires

The subject questionnaires and the VAS used in this study will be entered by the subject directly in an electronic patient reported outcomes (ePROs) device or on paper copy. All subject reported outcome data will be provided in English or Spanish and instructions will be provided in the subject's local language. The questionnaires and the VAS will be reviewed for completeness by the study site staff and subjects will be requested to complete any missing information.

Symptoms or worsening of symptoms documented on any of the questionnaires or the VAS do not need to be documented as additional AEs because the questionnaires and the VAS will be analyzed as part of the final report. However, it is at the discretion of the Investigator to decide whether to document such symptoms as additional AEs. The main source for AE collection will be the face-to-face interview between the subject and study site staff, using open, non-directive questions (Section 8.2).

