6.2.4 Stopping Rules for Investigational Product

For safety purposes, smoking should be temporarily stopped in the event of any signs suggesting nicotine overexposure, (e.g., gastrointestinal disturbance [nausea, vomiting, diarrhea, stomach or abdominal pain], cold sweats, headache, dizziness, and breathing problems) or any reasons at the discretion of the Investigator.

Data and information contained in this document are considered to constitute trade secrets and confidential commercial information, and the legal protections provided to such trade secrets and confidential information are hereby claimed under the provisions of United States law. No part of this document may be publicly disclosed without the written consent of Philip Morris International.

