7.4 Clinical Assessments

Any clinically relevant medical condition detected during the Screening Visit has to be documented as a concomitant disease. This also applies to clinically relevant findings in laboratory values, vital signs, and ECGs detected during the Screening Visit. Any untoward medical occurrence in a subject detected during the study which was not present at the Screening Visit must be documented as an AE. Worsening of a pre-existing condition from the Screening Visit onwards will also be documented as an AE. If a clinically relevant finding is detected during the Screening period, the Investigator or designee needs to check if inclusion criterion No. 04 is still fulfilled.

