8.2.1 Collection of Information

Adverse event information will be collected from the time of signature of the ICF/Subject Information Sheet onwards until EOS either by the Investigator or designee via spontaneous reporting or by the use of consistent, open, non-directive questions from study site staff (e.g., “Have you had any health problems since the previous visit/How are you feeling since you were last asked?”). At the discretion of the Investigator or designee, the collection of AE information may also be triggered from the review of the subject questionnaires and the VAS. However, during the confinement period and during the ambulatory visits, the main source for AE collection will be face-to-face interview(s) with the subject.

Information recorded will include: verbatim description of the AE, start and stop dates and times, seriousness, severity (intensity), action taken (e.g., whether or not the AE led to the subject’s withdrawal from the study), and outcome (e.g., resolved, withdrawal due to AE).

For each AE, the intensity will be graded on a 3-point intensity scale (mild, moderate, severe) using the definitions provided in Section 8.2.5.

Any exacerbation/worsening or increased frequency of an AE or pre-existing condition shall be evaluated and recorded.

Correct medical terminology/concepts are preferred when recording AE terms, and abbreviations must be avoided. Wherever possible, a diagnosis is to be used to describe an AE as a diagnosed medical condition rather than individual signs and symptoms (e.g., record ‘pneumonia’ rather than ‘fever’, ‘cough’, ‘pulmonary infiltrate’ or ‘septicemia’ rather than ‘fever’ and ‘hypotension’ following blood sample).

Any AE that meets the serious criteria must be recorded both on the AE report form of the eCRF and on a separate SAE report form (Section 8.3).

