### 7.3.5 Minnesota Nicotine Withdrawal Scale (revised edition) Questionnaire

The MNWS (**Hughes and Hatsukami 2008**) is a 24 hour recall that will be completed by the subject him/herself daily from Day 0 to Day 6, and on the second day of every visit during the ambulatory period. From Day 0 to Day 6 only, MNWS questionnaire must be asked prior to start of product use/smoking and no later than 10:00 AM. On Day 31 and Day 61 the assessment of MNWS will be conducted irrespective of the time of product use but no later than 10:00 AM. Whilst on Day 91 the assessment of MNWS has to be conducted prior to smoking but no later than 10:00 AM.

The self-reported part of the MNWS consists of the following 15 items which are rated over the last 24 hours on a scale of 0 to 4 (see **Table 7**). Higher scores indicate greater intensity on that scale.

The total scores will be derived by calculating the average of all the non-missing data from the first 9 items. If more than 50% of the first 9 items are missing then the total score will be set to missing.

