#### 12.6.3.2.4 Minnesota Nicotine Withdrawal Questionnaire

The MNWS will be administered daily from Days 0 to 6, and Days 31, 61 and 91 for the assessment of Day-1 to Day 5, and Days 30, 60 and 90 as it is a 24-hour recall questionnaire.

All summaries, profiles and analysis will be presented for the THS 2.2 Menthol, mCC and SA arms.

The total score, along with the percent change from baseline will be summarized. The answers to the individual questions, along with the total score, the changes and percent changes from baseline will be listed.

The profiles of the raw means from baseline to Day 90 for the total scores will be plotted.

The analysis will compare each post baseline timpoint separately for the total score. An ANCOVA model will be used with terms for baseline score, sex, average daily mCC consumption over the last 4 weeks as reported during screening, and randomization arm,. No adjustment will be made for multiple comparisons.

The SAS code to be used is similar to the model reported in Section 12.6.1.3 "Sensitivity Analysis".

LS means for each product along with the difference (THS 2.2 Menthol - mCC) and (THS 2.2 Menthol – SA) with 95% CI will be presented in the tables.

All figures, summaries and analyses will be performed on the PP Set and FAS only.

The data will be presented in the below outputs:

TFL number	Title
FIGURES	
15.1.2.8.1	MNWS Total Score Arithmetic Mean and 95% CI – PP Set
15.1.2.8.2	MNWS Total Score Arithmetic Mean and 95% CI – FAS
15.1.2.9.1	MNWS Total Score Arithmetic Least Squares Means and 95% CI – PP Set
15.1.2.9.2	MNWS Total Score Arithmetic Least Squares Means and 95% CI – FAS
TABLES	
15.2.4.56.1	Descriptive Statistics of MNWS Total Score – PP Set
15.2.4.56.2	Descriptive Statistics of MNWS Total Score – FAS
15.2.4.57.1	Analysis of MNWS Total Score – PP Set
15.2.4.57.2	Analysis of MNWS Total Score – FAS
LISTINGS	
15.3.6.15	Listing of MNWS Questionnaire Results and Changes from Baseline

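### Questionnaire symptoms are excused from AE recording because the questionnaires will be analysed, but five MNWS symptoms have no planned Safety Population summary unless an AE is entered

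*Protocol*

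**What the plan says.** **AE recording.** Protocol 7.8.3 says: "Symptoms or worsening of symptoms documented on any of the questionnaires or the VAS do not need to be documented as additional AEs". The reason follows directly: "because the questionnaires and the VAS will be analyzed as part of the final report". The same paragraph adds that "it is at the discretion of the Investigator to decide whether to document such symptoms as additional AEs", and names the face-to-face interview as the main source of AEs. Protocol 8.2.1 agrees: at the investigator's discretion, AE collection "may also be triggered from the review of the subject questionnaires and the VAS". Protocol 7.4 sets a general rule without reference to 7.8.3: "Any untoward medical occurrence in a subject detected during the study which was not present at the Screening Visit must be documented as an AE".

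**MNWS scoring and reporting.** The MNWS has 15 self-reported items, each rated 0 to 4 for the previous 24 hours. SAP 7.3.5 states: "The total scores will be derived by calculating the average of all the non-missing data from the first 9 items". SAP Table 7 excludes items 10 to 15 from the total: constipation, dizziness, coughing, dreaming or nightmares, nausea and sore throat. SAP 12.6.3.2.4 summarises and models the total score, on the PP Set and FAS only. For the items it says: "The answers to the individual questions, along with the total score, the changes and percent changes from baseline will be listed".

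**Standing of the symptoms.** Nausea and dizziness appear in Protocol 6.2.4 among "any signs suggesting nicotine overexposure, (e.g., gastrointestinal disturbance [nausea, vomiting, diarrhea, stomach or abdominal pain], cold sweats, headache, dizziness". Protocol 2.3.3 lists withdrawal symptoms as a foreseeable risk.

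**The concern.** The permission not to record an AE rests on the symptom being reported elsewhere. If the questionnaire item never reaches a summary, that ground fails. Whether a reader sees the symptom by arm then depends on someone choosing to enter an AE, in an open-label trial. At stake is the completeness of arm-level safety reporting for symptoms that the protocol itself connects with nicotine overexposure or withdrawal, and for throat irritation. Protocol 7.4 and 7.8.3 also give the site different answers for a new symptom that first appears on a questionnaire. No primary endpoint, sample size or confirmatory test is involved.

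**Working it through.** The plan states no figure to reproduce. The check traces each MNWS item outside the total to every planned output that could show it by arm.

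**1. Is there an implied summary?** No. SAP 12.1 limits summary statistics and analyses to data for which the SAP details them. SAP 12.6.4 does not include the MNWS among the safety variables. Listing 15.3.6.15 is therefore the only MNWS output in which items 10 to 15 appear.

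**2. Where else could the six symptoms appear, apart from AE tables?**

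| MNWS item | Other planned arm-level output | Remaining gap |
|---|---|---|
| Coughing | Cough assessment, Tables 15.2.6.25 and 15.2.6.25.1, Safety Population (SAP 12.6.4.4.6) | None |
| Dizziness, nausea | MCEQ items 9 and 10, averaged as Aversion (SAP Table 6); PP Set and FAS; not collected in SA (SAP 12.6.3.2.3) | No separate symptom summary and no Safety Population table; nothing in SA |
| Constipation, dreaming or nightmares, sore throat | None | All arms |

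The MCEQ items ask whether smoking caused the symptom, which is narrower than the MNWS question.

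**3. How much data is left to a listing?**

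- Scheduled MNWS assessments: Days 0 to 6 (7) plus Days 31, 61 and 91 (3) = 10.
- The Day 0 and Day 1 assessments are completed before first assigned product use, and they recall Day -1 and Day 0. They cannot reflect the assigned arm. Post-baseline assessments: 10 − 2 = 8.
- Items: 6 outside the total − 1 (coughing) = 5.
- Subjects: 160 in total, 40 of them in SA (SAP Table 1).

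Upper bound, five items in all arms: 160 × 8 × 5 = **6,400** responses.

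Counting dizziness and nausea only where no other summary exists (SA): 160 × 8 × 3 + 40 × 8 × 2 = 3,840 + 640 = **4,480** responses.

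Both counts assume every subject completes every assessment. They count questionnaire answers, most of which may be zero. They do not count adverse events.

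**4. The two AE statements side by side.** Protocol 7.4 makes recording mandatory for a new untoward occurrence and also requires worsening of a pre-existing condition to be recorded. Protocol 7.8.3 makes recording of new or worsening questionnaire symptoms optional. Neither section says which governs when a symptom meets both descriptions.

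**The case against.** The strongest reply is that the MNWS is not the route by which AEs are meant to be found. Interviews are the main source (Protocol 7.8.3 and 8.2.1). AEs are actively collected from Admission to Discharge (Protocol 8.2.4), and the Section 9 schedules include AE questioning on each confinement day and at each ambulatory visit. SA subjects are closely monitored for signs and symptoms of withdrawal (Protocol 7.3). A subject who mentions nausea at interview can enter the SOC and PT tables by arm. In the two product arms, MCEQ Aversion is compared by ANCOVA with 95% CIs at each post-baseline time point. The MNWS is an exploratory endpoint, and Protocol 7.8.3 promises analysis of the questionnaires, not item-level safety tables. Protocol 7.4 can be read as the general rule and 7.8.3 as a specific provision for self-completed forms.

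Much of this stands. A reader might infer that all six items can miss every safety table; that is wrong for coughing. A reader might also infer that questionnaire symptoms are barred from AE recording, or that they will be under-reported differently by arm or site. The documents do not support either: recording remains possible, and nothing in them shows a differential loss.

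The reply does not close the gap. The interview questions are open and non-directive, AE collection prompted by a questionnaire is discretionary, and staff are told to review the questionnaires only for completeness. The excuse in 7.8.3 is justified by analysis of the questionnaires, and for these five items that analysis is a listing.

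**Conclusion.** The point holds for five MNWS items, not six. Constipation, dreaming or nightmares, and sore throat in every arm, and dizziness and nausea in the SA arm, have no planned arm-level summary unless an AE is entered. In the THS and mCC arms, dizziness and nausea are seen only as a two-item average outside the Safety Population.

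The number of AEs that could go unrecorded cannot be derived from the documents. The measurable size is at most 6,400 post-baseline responses left to a listing, or 4,480 on the narrower count, assuming 160 subjects with complete follow-up. A count of all six items at all ten assessments (160 × 10 × 6 = 9,600) would be tempting, but it includes coughing, which is tabulated, and two assessments that precede assigned product use.

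The consequence is limited to safety reporting. It merits a change because the stated reason for 7.8.3 fails for these items, because 7.8.3 and 7.4 are inconsistent, and because the remedy is cheap.

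**What to change.** Add one descriptive table on the Safety Population to SAP 12.6.3.2.4 or to the safety section. It should show, by arm (all three) and assessment day, MNWS constipation, dizziness, dreaming or nightmares, nausea and sore throat, with n (%) at each score 0 to 4 and n (%) worsened from baseline. Coughing need not be repeated.

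Reconcile the AE-recording statements in Protocol 7.8.3 and 7.4 so that they do not contradict each other for a symptom first reported on a questionnaire. Which statement should prevail is for the sponsor and investigators.

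The cost is one table from data already collected, plus a sentence of clarification, with no new assessments. The table is long: 5 items × 9 time points (baseline and eight post-baseline) × 5 scores × 3 arms = 675 cells before the worsening counts. It is a single repeated template. If the SAP is already final, SAP Section 3 allows supplementary analyses to be described in the CSR.

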7.8.3.1 Fagerström Test for Nicotine Dependence (revised version)

Potential nicotine dependence will be assessed via a questionnaire at Screening and on Day 90 Visit (Day 90) using the Fagerström Test for Nicotine Dependence (FTND) in its revised version (Fagerström et al., 2012).

The questionnaire consists of six questions which will be answered by the subject himself/herself. The scores obtained on the test permit the classification of nicotine dependence into three levels: Mild (0-3 points), moderate (4-6 points), and severe (7-10 points) (Fagerström et al., 2012).

7.8.3.2 Assessment of Cough

Subjects will be asked to assess the respiratory symptom 'cough' on a VAS, on three Likert scales, and with an open question on a daily basis during the confinement period (from Day 0 to Day 6), and at every visit on Day 30 Visit (Day 31), Day 60 Visit (Day 61) and Day 90 Visit (Day 91). From Day 0 to Day 6 only, assessment of cough must be done prior to start of

Data and information contained in this document are considered to constitute trade secrets and confidential commercial information, and the legal protections provided to such trade secrets and confidential information are hereby claimed under the provisions of United States law. No part of this document may be publicly disclosed without the written consent of Philip Morris International.

product use/smoking and no later than 10:00 AM. On Day 31 and Day 61, and Day 91, assessment of cough will be conducted irrespective of the time of product use but no later than 10:00 AM.

Subjects will be asked if they have experienced a regular need to cough, e.g., whether they have coughed several times in the previous 24 hours prior to assessment. If the answer is 'yes', subjects will be asked to complete a VAS, 3 Likert scales, and to answer the open question.

On the VAS, subjects will assess how bothersome their cough was during the previous 24 hours. The VAS ranges from 'not bothering me at all' to 'extremely bothersome.'

Furthermore, subjects will assess the intensity and frequency of cough and the amount of sputum production during the previous 24 hours on Likert scales.

The intensity of cough will be assessed on a 5-point Likert scale ranging from 1 to 5, with 1 = very mild – 2 = mild – 3 = moderate – 4 = severe – 5 = very severe.

The frequency of cough will be assessed on a 5-point Likert scale ranging from 1 to 5, with 1 = rarely – 2 = sometimes – 3 = fairly often – 4 = often – 5 = almost always.

The amount of sputum production will be assessed on a 4-point Likert scale ranging from 0 to 3, with 0 = no sputum – 1 = a moderate amount of sputum – 2 = a larger amount of sputum – 3 = a very large amount of sputum.

Finally, subjects will be asked to share any other important observations with the staff about their coughing.

7.8.3.3 *Modified Cigarette Evaluation Questionnaire*

Product evaluation will be assessed using the Modified Cigarette Evaluation Questionnaire (MCEQ) (Cappelleri et al., 2007). The MCEQ assesses the degree to which subjects experience the reinforcing effects of smoking, by measuring:

- Smoking satisfaction (satisfying, tastes good, enjoys smoking).
- Psychological rewards (calms down, more awake, less irritable, helps concentrate, reduces hunger).
- Aversion (dizziness, nauseous).
- Enjoyment of respiratory tract sensations (single-item assessment).
- Craving reduction (single-item assessment).

Data and information contained in this document are considered to constitute trade secrets and confidential commercial information, and the legal protections provided to such trade secrets and confidential information are hereby claimed under the provisions of United States law. No part of this document may be publicly disclosed without the written consent of Philip Morris International.

The MCEQ will be completed by subjects during the confinement period on a daily basis from Day -1 to Day 5 and on every ambulatory visits on Day 30 Visit (Day 30), Day 60 Visit (Day 60), and Day 90 Visit (Day 90). On Day -1 and Day 0, all subjects will complete the questionnaire. From Day 1 onwards, only subjects who are randomized to the THS 2.2 Menthol and mCC arms will complete this questionnaire. The subjects will complete the questionnaire by themselves.

7.8.3.4 *Questionnaire of Smoking Urges (QSU-brief)*

To assess the urge-to-smoke, all subjects will be asked to fill-in a 10-item brief version of the QSU (Cox et al., 2001). The QSU-brief is a self-reported questionnaire with 10 items to be rated on a 7-point scale, ranging from 1 (strongly disagree) to 7 (strongly agree). Higher scores in this questionnaire indicate a higher urge to smoke.

The QSU-brief will be completed by the subject himself/herself on a daily basis from Day -1 to Day 5, and on every visit during the ambulatory period, i.e., Day 30 Visit (Day 30), Day 60 Visit (Day 60), and Day 90 Visit (Day 90).

7.8.3.5 *Minnesota Nicotine Withdrawal Scale (revised version)*

The MNWS revised version is a valid and reliable scale that has been used previously to examine signs and symptoms of withdrawal from cigarette smoking (Hughes et al., 1986, Hughes et al., 2008). It consists of 2 scales: a 'self-report scale' and an 'observer scale.'

For the purpose of this study, only the self-reporting scale will be used and filled-in by the subject. Furthermore, the subject's weight will not be recorded for the purpose of the MNWS. At the end of the assessment of the questionnaire, the subject's pulse rate will be recorded.

Subjects will be asked to rate the items for the previous 24 hours on a scale ranging from 0 to 4 (where 0 = none, 1 = slight, 2 = mild, 3 = moderate, 4 = severe).

The MNWS (revised version) will be completed on a daily basis from Day 0 to Day 6, and at every visit during the ambulatory period, i.e., Day 30 Visit (Day 31), Day 60 Visit (Day 61) and Day 90 Visit (Day 91). From Day 0 to Day 6 only, MNWS questionnaire must be asked prior to start of product use/smoking and no later than 10:00 AM. On Day 30 Visit (Day 31), Day 60 Visit (Day 61), and Day 90 Visit (Day 91), assessment of MNWS will be conducted irrespective of the time of product use but no later than 10:00 AM.

HST Questionnaire

A specific questionnaire, used for exploratory purposes has been developed to evaluate the impact of the utilization of the HST SODIM® device on smoker's smoking/inhalation experience in terms of ritual disruption.

Data and information contained in this document are considered to constitute trade secrets and confidential commercial information, and the legal protections provided to such trade secrets and confidential information are hereby claimed under the provisions of United States law. No part of this document may be publicly disclosed without the written consent of Philip Morris International.

This is a questionnaire with 5 items to be rated on a 5-point scale and open questions. Subjects will be asked by the Investigator to complete the HST questionnaire on:

- Day 0 for all subjects smoking mCC compatible with the HST SODIM® device (i.e., non-slim mCC)
- Day 4, Day 30 Visit (Day 30), Day 60 Visit (Day 60), and Day 90 Visit (Day 90) for all subjects in the THS 2.2 Menthol and mCC arms (except mCC which are not compatible with the HST SODIM® device).

7.8.3.6 *Socio-Economic Status*

As part of the characterization of the study population it is important to measure variables that have been shown to be related to nicotine dependence and product reinforcing value. Based on prior tobacco research these factors include age, gender, ethnicity, tobacco use history, educational as well as socio-economic status.

Socio-economic status (SES) information is recorded in similar manner in the clinical program, in behavioral research and will be eventually assessed in postmarked studies once the product is commercialized. In order to predict and evaluate the effect of alternative, potentially less harmful tobacco product use might have in adult smokers the socio-economic status constitutes an important demographic characteristic. SES data will be reported across the randomized clinical studies and will be collected in observational pre-market and post-market studies. At screening the subjects will be informed in detail about the exams and evaluations planned during the study, and similarly notified about the SES assessment which will be done on Day 4 once they provided informed consent and were enrolled into the study.

On Day 4, subjects will fill a questionnaire, which will allow the Sponsor to determine subject's Socio-Economic Status (SES). Subjects will be asked a series of questions related to their education, occupational status, size and annual income of their household. These data will be used to create a measure for SES that categorizes subjects into low, moderate and high SES (King et al., 2011). The method used to create SES tertiles will be described in the SAP. If the subject does not want to answer the questionnaire, he will not be withdrawn from the study.

7.8.3.7 *Current and Past Smoking Behavior*

Subjects will be assessed for their current and past smoking behavior at baseline on Day -1 and on Day 5 by the means of 2 questionnaires. The questionnaires will be asked with the following sequence:

- A standard questionnaire (Behavioral Risk Factor Surveillance System Questionnaire 2011) (CDC, 2011a) which is validated.

Data and information contained in this document are considered to constitute trade secrets and confidential commercial information, and the legal protections provided to such trade secrets and confidential information are hereby claimed under the provisions of United States law. No part of this document may be publicly disclosed without the written consent of Philip Morris International.

- A Smoking Questionnaire (SQ) to be validated. Immediately after the administration of the SQ, some supplemental questions will be collected on the completion of the SQ questionnaire.

The Behavioral Risk Factor Surveillance and the SQ are self-administrated to be answered by subjects. The supplemental questions will be asked by the site.

The standard questionnaire is the questionnaire used in Behavioral Risk Factor Surveillance System Questionnaire 2011 (CDC, 2011a), Section 7 on tobacco use. The standard questionnaire consists of 5 questions. All 5 questions are close-ended questions and the responses are exhaustive and mutually exclusive.

- Question 1 collects information on the 100 cigarettes criterion.
- Question 2 allows for a broad classification of current cigarette smoking behavior (daily, occasional, non).
- Question 3 captures quitting experience during past 12 months.
- Question 4 records past smoking duration.
- Question 5 provides information regarding other tobacco use e.g. smokeless tobacco.

The SQ focuses on self-reported current and past cigarette smoking behavior. The SQ consists of 8 questions. The first 3 questions are close-ended questions and the responses are exhaustive and mutually exclusive. The last 5 questions refer to the individual smoking history and are answered to the degree applicable.

- Question 1 allows for a broad classification of current cigarette smoking behavior (daily, occasional, ex, non).
- Questions 2 and 3 collect information on the 100 cigarettes criterion and on ever smoking (defined as smoking at least one cigarette per day).
- Question 4 captures age of initiation and Questions 5 and 6 capture the current as well as total quitting duration, respectively.
- The brand of cigarettes predominantly smoked in the last 12 months of smoking is captured in Question 7.
- Question 8 captures the tobacco smoking history. Daily numbers of manufactured cigarettes, as well as hand-rolled cigarettes, cigars, and pipes consumed, separately for seven time periods.

Finally, the supplemental questions consist of 8 questions. This supplemental question 1 is related to the time which the subject spends to complete the SQ. Question 2-7 are close-

ended questions and to be answered yes or no. Question 8 is open-end allowing for addition comments provided by subjects.

The daily mCC consumption reported in these questionnaires will not be used for eligibility. The data from these questionnaires will be described as part of the CSR and further analysis will be the subject of a separate report.

7.8.3.8 *Prochaska ‘Stage of Change’ Questionnaire: Intention to Quit Smoking*

The Prochaska ‘Stage of Change’ questionnaire will be used to assess the smokers’ mental state for the intention to quit (7.4.4 and Appendix 5 for staging algorithm; DiClemente et al., 1991 and Velicer et al, 1995). There are 5 stages of change describing smokers and former smokers: 1. Precontemplation, 2. Contemplation, 3. Preparation, 4. Action and 5. Maintenance. In the *precontemplation* stage, the individual does not recognize smoking as a problem.

In the *contemplation* stage, the individual is gathering information about smoking, such as contacting a health care provider, or tobacco quit line for information on the effects of smoking or cessation classes. During this stage, the stress and inconvenience of quitting smoking is greater than the immediate and possible long-term health effects from continued smoking. In the *preparation* stage, intention and behavior begin to come together and the subject is preparing to enter the action stage in the next 30 days. It is necessary for the subject to recognize the benefits of not smoking, before a subject can enter the *action* stage and as a result, change their smoking behavior. After six months of not smoking, the individual reaches the *maintenance* stage when different skills may be needed to prevent relapse from those employed in the initial behavior change.

The Prochaska ‘Stage of Change’ questionnaire will be performed at Screening, Admission (Day -2), Day 30 Visit (Day 30), Day 60 Visit (Day 60) and at Day 90 Visit (Day 90). The Prochaska ‘Stage of Change’ questionnaire will be asked to the subject prior to product trial.

